PROTOCOL TITLE

Neuromodulation of placebo and nocebo effects

IDENTIFIER

NCT03102710

DATE

4/30/2019

SPECIFIC AIMS

Specific Aim 1: Characterize the effect of applying tDCS to the rDLPFC to modulate placebo and nocebo effects in healthy subjects

Hypothesis 1.1: In the sham tDCS group, placebo lidocaine and capsaicin will produce a significant pain rating decrease (placebo) and increase (nocebo) respectively, in response to identical heat pain stimuli as compared to a within-subject control “neutral” cream. Both effects will be augmented by tDCS enhancement of rDLPFC excitability and blunted by tDCS inhibition of rDLPFC excitability.

Hypothesis 1.2 In the sham tDCS group, placebo treatment will produce fMRI signal increases in regions associated with the DPMS including the DLPFC, orbital prefrontal cortex (OPFC), rostral anterior cingulate cortex (rACC), periaqueductal gray (PAG), and fMRI signal decreases in pain intensity sensitive regions (insula and secondary somatosensory cortex, S2), as compared to the within-subject control in response to identical pain stimuli. These changes will increase in the tDCS enhancement cohort and blunt in the inhibition cohort.

Hypothesis 1.3 In the sham tDCS group, nocebo treatment will produce fMRI signal increases in brain regions associated with cognition and anxiety, including DLPFC, hippocampus, and OPFC, along with fMRI signal decreases in the areas associated with the affective component of pain (dorsal anterior cingulated cortex (dACC) and insula), as compared to the within-subject control neutral cream. These fMRI signal changes will be blunted in the tDCS inhibition group and increased in the tDCS enhancement group.

Specific Aim 2: Characterize how tDCS to rDLPFC can modulate functional connectivity of rDLPFC

Hypothesis 2: Enhancing rDLPFC excitability will increase resting state functional connectivity (rsFC) between the rDLPFC and rACC and insula whereas inhibiting rDLPFC excitability will decrease rsFC between the rDLPFC and rACC and insula as compared with sham tDCS. The rsFC between rDLPFC and rACC will be associated with placebo effect as indicated by pain rating difference.

STUDY PROCEDURES

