We will recruit healthy subjects for this study. Please see the [Protection of Human Subjects](#) section for detailed entry criteria for screening and recruitment. In this experiment, subjects will be randomly assigned to three groups (26 per group): 1) tDCS enhancement group to increase the excitability of rDLPFC, 2) tDCS inhibition group to decrease the excitability of rDLPFC, and 3) sham tDCS group.

Subjects will participate in five experimental sessions: a training and familiarity session, contextual learning/expectancy boost session, two tDCS sessions, and a session combining tDCS and testing for placebo/nocebo effects. Sessions 1 and 2 will be separated by 2-5 days, sessions 2 and 3 will be separated by 1-5 days, then sessions 3, 4, and 5 will be applied on consecutive three days. We will measure tDCS effects via changes in subjective pain ratings, fMRI signals in response to calibrated heat pain and the rsFC.

Detailed experimental procedure

Noxious heat stimuli will be delivered using a PATHWAY system (Medoc Advanced Medical Systems). All stimuli will be initiated from a baseline temperature of 32 °C and increased to a target temperature. Each stimulus will be presented for 12 seconds, including 2.5 seconds to ramp up to the target temperature and 2.5 seconds to ramp down to baseline again. Heat stimuli will be applied to the right volar forearm. **In sessions where tDCS is applied we will administer the tDCS sensation questionnaire to ensure subjects did not have any unexpected adverse reactions.**

Randomization Subjects will be randomized into one of three groups using a centrally generated variable-sized block design: tDCS enhancement, tDCS inhibition, and sham tDCS groups.

Session 1 is a training, familiarity, and calibration session. Subjects will be trained to use the Sensory Gracely Scale (0-20) [1, 2] to rate pain experiences using the same method as in our previous studies [3, 4]. Subjects will first receive an ascending heat stimulus sequence (starting from 38 degrees). The three temperatures that each subject rates as approximately 5-6 (mild pain), 10-11 (moderate pain) and 14-15 (strong pain) will be selected. Subjects will receive a urine drug test on this day to determine no substance abuse.

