Using methods similar to those of previous studies [5, 6], subjects will then be told that to test the hyperalgesia effect of capsaicin and the analgesia effect of the lidocaine, 6 identical pain stimuli will be applied to each of the nine spots. However, in reality, to boost subjects' expectancy, 6 *moderate* stimuli will be given to each of the neutral control cream spots, 6 *mild* stimuli will be applied on placebo Lidocaine cream spots, and 6 *high* stimuli will be applied on nocebo Capsaicin cream spots. The location of the placebo, nocebo and control rows will be randomized across subjects to balance the experimental design. Subjects will be asked to rate their expectancy of both the analgesic effect of lidocaine cream and the hyperalgesic effect of capsaicin using a 0-10 scale (with 0 indicating a very negative expectation of “does not work at all” and 10 indicating a very positive expectation of “very effective”) before the pain stimulus is applied and again how much they expected the cream reduced or enhanced their pain afterward. The Gracely Sensory and Affective Scale will be used to rate experienced pain during the stimulation afterward.

Session 3 is the first tDCS session. Right before and after tDCS, resting state fMRI data will be collected.

Session 4 is the second tDCS session with no fMRI scan involved.

Session 5 is the third tDCS and placebo / nocebo test session. At the beginning of the Session, subjects will be told that the Session 2 procedure will be repeated in the fMRI scanner. As in Session 2, the 3 different creams (in reality all one inert cream) will be administered to each row of squares, with “lidocaine” and “capsaicin” cream administered to the same rows as determined in Session 2. Then, tDCS will be applied based on subjects' randomization. The resting state fMRI data will be collected before and after tDCS.

After that, calibrated pain will be applied during the fMRI scan. Since this session will test the placebo/nocebo effect, we will only administer different heat stimuli to the 3 regions in the most lateral column of the 9 x 9 grid. Then, subjects will be asked to rate their expectancy of both the analgesia effect of lidocaine cream and the hyperalgesic effect of capsaicin using a 0-10 scale. After that, we will administer the same moderate stimulus to all remaining regions with all 3 creams. Our outcome measurement will be the subjective pain ratings and fMRI signal changes to identical calibrated heat pain.

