Specific Aim 2: Characterize the neural mechanisms by which tDCS to rDLPFC modulates functional connectivity of the rDLPFC

Primary outcome: rDLPFC functional connectivity changes before and after different tDCS intervention

Seed based functional connectivity analysis Seed based FC will be applied with a method used in our previous studies [3, 7-10]. In summary, the fMRI data will be preprocessed using Data Processing Assistant for Resting-State fMRI (DPARSF) software [11, 12]. The preprocessing will include slice timing correction, head-motion correction, spatial registration to respective structural images for each subject, 6 rigid body motion, white matter and cerebrospinal fluid signals will be regressed out. After linear de-trending, data will be filtered using a temporal bandpass (0.01-0.08 Hz), and finally smoothed using a full width half maximum of 6 mm. FC analysis for individual subjects will be carried out in DPARSF by applying the seed-based approach. In this study, we will use rDLPFC [13, 14] as seed.

Group analysis will be performed using the random effect model with SPM8. A full factorial model module in SPM8 will be applied: three groups (excitability enhancement, inhibition and sham), two tDCS (first and third) with two conditions (pre and post-treatment). To investigate the incremental effect across the first and last tDCS, we will compare pre- and post-treatment differences in tDCS 1 and 3 of each group. To investigate the incremental effect across three time points, we will also apply the same analysis on the pre-tDCS rsFC in tDCS 1 and 3. In addition, a multiple regression analysis will be performed between the placebo and nocebo effects (indicated by subjective pain rating differences between Lidocaine / Capsaicin and the control condition) and rsFC after the third tDCS by pooling the data of all three groups (group indicator will be included in the model as a covariate). LOT, ERS, STAI scores, gender, and experimenter effect will also be included as covariates in the analysis. A threshold of $p < 0.005$ will be applied for the region of interest. A threshold of $p < 0.001$ uncorrected and $p < 0.05$ corrected will be used for non-ROI brain areas.

Reference

-
1. Kong, J., R.L. Gollub, G. Polich, I. Kirsch, P. Laviolette, M. Vangel, B. Rosen, and T.J. Kaptchuk, *A functional magnetic resonance imaging study on the neural mechanisms of hyperalgesic placebo effect*. J Neurosci, 2008. **28**(49): p. 13354-62 PMCID: PMC2649754.

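### For the first tDCS session, Aim 2 compares arms on raw connectivity change without adjusting for the pre-tDCS scan, which loses precision but adds no bias

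*SAP*

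**What the plan says.** The SAP (Specific Aim 2) names as primary outcome "rDLPFC functional connectivity changes before and after different tDCS intervention". The group model is a full factorial in SPM8 with the factors "three groups (excitability enhancement, inhibition and sham), two tDCS (first and third) with two conditions (pre and post-treatment". For the effect across the first and last stimulation, the SAP says "we will compare pre- and post-treatment differences in tDCS 1 and 3 of each group".

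That last phrase leaves the comparison between arms implicit. It follows from the group factor and from Hypothesis 2 in the protocol, which predicts that inhibition "will decrease rsFC between the rDLPFC and rACC and insula as compared with sham tDCS" and that enhancement does the opposite.

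On covariates the SAP says "LOT, ERS, STAI scores, gender, and experimenter effect will also be included as covariates in the analysis". Whether this covers the factorial or only the regression described just before it, pre-tDCS connectivity is not on the list. The SAP analyses the pre-tDCS scans of tDCS 1 and 3 separately, but as an outcome.

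For Session 3 the protocol says "Right before and after tDCS, resting state fMRI data will be collected". Before that, all subjects have had only the sham stimulation of Session 2. The Session 5 pre-tDCS scan, in contrast, follows two randomised stimulation sessions.

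**The concern.** When pre and post are two levels of a factor, the arm-by-condition contrast within Session 3 is the difference between arms in mean raw change. That fixes the slope on the pre-scan at 1. Unless the pre-scan predicts the post-scan with a slope of 1, subtracting it in full carries some of its noise into the outcome. Regression lets the data choose the slope.

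Hypothesis 2 rests on two named connections, with 26 subjects per arm and a threshold of 0.005. Neither document gives a power calculation. If the correlation between the two scans is modest, the Session 3 comparison has wider intervals and less power than the same two scans allow.

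**Working it through.** **Inputs from the documents.** Three arms, 26 per group (protocol, Study Procedures), so 78 in total. Region-of-interest threshold p < 0.005, sidedness not stated (SAP, Specific Aim 2). The 26 per group comes with no effect size, SD or power, so there is no planned figure to reproduce.

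**Assumptions.** Pre-post correlation rho from 0.3 to 0.9; equal variances at pre and post, set to 1; two-sided testing; an active-versus-sham difference of 0.6 SD.

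**Step 1, same target.** Arms are randomised and the Session 3 pre-scan precedes arm-specific stimulation, so its expected value is the same in every arm. Raw change and the adjusted post-scan therefore estimate the same Session 3 arm effect.

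**Step 2, variance per subject.** Raw change: 2(1 - rho). Post adjusted for pre: 1 - rho². The ratio, adjusted to raw, is (1 + rho)/2. The excess of raw change is 2(1 - rho) - (1 - rho²) = (1 - rho)², which is positive for every rho below 1.

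**Step 3, standard error and power.** The SE of a two-arm difference is √(2V/26), with V from Step 2. The equivalent n is the number per arm that raw change would need to match adjustment with 26, that is 26 divided by the variance ratio. Power uses the noncentral t at 0.005 with 75 df (raw) and 74 df (adjusted). For power, the adjusted variance is multiplied by 1 + 1/73 = 1.014, the expected cost of chance imbalance in the covariate.

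| rho | V raw | V adjusted | ratio | SE raw | SE adjusted | SE fall | equivalent n | power at 0.6 SD |
|---|---|---|---|---|---|---|---|---|
| 0.3 | 1.40 | 0.91 | 0.65 | 0.328 | 0.265 | 19% | 40.0 | 15% to 27% |
| 0.5 | 1.00 | 0.75 | 0.75 | 0.277 | 0.240 | 13% | 34.7 | 24% to 35% |
| 0.7 | 0.60 | 0.51 | 0.85 | 0.215 | 0.198 | 8% | 30.6 | 47% to 55% |
| 0.8 | 0.40 | 0.36 | 0.90 | 0.175 | 0.166 | 5% | 28.9 | 70% to 75% |
| 0.9 | 0.20 | 0.19 | 0.95 | 0.124 | 0.121 | 2.5% | 27.4 | 97% to 98% |

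The SE columns leave out the 1.014 factor. Below rho 0.5, V raw exceeds 1, so raw change is noisier than the post-scan alone. For an assumed 0.8 SD difference, power goes from 33% to 55%, 50% to 66% and 79% to 86% at rho 0.3, 0.5 and 0.7.

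**Step 4, simulation.** With 6,000 replicates of three arms of 26, the variance ratios were 0.64, 0.76, 0.86 and 0.96 at rho 0.3, 0.5, 0.7 and 0.9, in line with (1 + rho)/2.

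**Step 5, where the result stops.**

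- *Pooling over both sessions.* If all four scans are equally correlated, the change averaged over two sessions has variance 1 - rho. The single-session adjusted estimate has 1 - rho², which is 1 + rho times as much: 1.3, 1.5 and 1.7 times at rho 0.3, 0.5 and 0.7.
- *Session 5 post adjusted for Session 3 pre.* Raw change depends on the same-day correlation, the adjusted estimate on the cross-day one. If these are 0.7 and 0.5 (assumed), the ratio is (1 - 0.25)/(2 × 0.3) = 0.75/0.60 = 1.25, so adjustment is noisier. At 0.6 and 0.4 it is 0.84/0.80 = 1.05; at 0.5 and 0.3 it is 0.91/1.00 = 0.91.
- *Session 5 post adjusted for Session 5 pre.* Suppose a total effect of 1.0, of which 0.5 is already present in the Session 5 pre-scan, and rho 0.5. The adjusted estimate is 1.0 - 0.5 × 0.5 = 0.75. That is neither the total effect (1.0) nor the third-session increment (0.5).

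**The case against.** The best defence is that the SAP defines its outcome as change, that raw change is unbiased under randomisation, and that the planned model covers two sessions, so a single-session comparison does not represent it. Much of this stands. A reader might infer three stronger claims that the documents do not support.

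- *The planned analysis is biased.* It is not. Randomisation protects both analyses at Session 3.
- *The planned model as a whole wastes precision.* This is not shown. A contrast pooled over both sessions can be more precise than the adjusted Session 3 estimate (Step 5). The two answer the same question only if the within-session effect is equal at both sessions, and the SAP does not say which contrast is primary.
- *The same adjustment improves Session 5.* It changes the question there. Adjusting for the Session 3 pre-scan gives the cumulative effect of three stimulations, not the within-session change the SAP asks for, and it may be noisier.

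It is also fair to say that the gain could be small. The documents give the resting scan length (8 minutes) but nothing on the reliability of the connectivity measure. None of this answers the Session 3 comparison taken alone: there the two analyses share an estimand, and the adjusted one has the smaller variance whenever rho is below 1, apart from the small cost of estimating the slope.

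**Conclusion.** The point holds for the arm comparison at the first tDCS session. Neither document plans a baseline-adjusted analysis of connectivity, and a valid baseline is already collected. The loss is material if rho is about 0.3 to 0.6 and minor near 0.9, and the documents cannot settle which applies. The figures rest on equal variances, two-sided testing and an assumed effect size; the direction of the Session 3 result does not depend on the effect size. This is a worthwhile improvement to the plan. It does not invalidate the Aim 2 analysis.

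**What to change.** For the rDLPFC-rACC and rDLPFC-insula connections, extract one connectivity value per scan. Estimate the Session 3 arm effect by regressing the Session 3 post-tDCS value on arm, with the Session 3 pre-tDCS value of the same connection as covariate. State this in the SAP before arms are compared.

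Keep the factorial for whole-brain maps, the Session 5 within-session change and any contrast pooled over sessions. If Session 5 post-tDCS connectivity is also adjusted for the Session 3 pre-scan, label the result as a separate, cumulative three-session effect. Do not adjust for the Session 5 pre-scan as if it were a baseline.

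The cost is one degree of freedom, one extra regression per connection, extraction of one value per scan, and a definition in the SAP of the rACC and insula regions from which the values are taken. No new data are needed.

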PROTOCOL TITLE

Neuromodulation of placebo and nocebo effects

IDENTIFIER

NCT03102710

DATE

4/30/2019

BIOSTATISTICAL ANALYSIS

Specific Aim 1: Characterize the neural mechanisms by which tDCS to rDLPFC modulates placebo / nocebo responses in healthy subjects in an acute pain paradigm.

Primary outcome: 1) fMRI signal changes evoked by identical experimental pain in different conditions (before and after different inert creams) after different tDCS interventions; 2) placebo and nocebo effect difference (as indicated by pain rating differences) after different tDCS interventions.

Similar to our previous studies [1-3], fMRI data processing and statistical analyses will be carried out using SPM8 (<http://www.fil.ion.ucl.ac.uk/spm/>). Preprocessing will include co-registration, motion correction, normalization to MNI stereotactic space, and spatial smoothing with an 8 mm Gaussian kernel. Then, for each subject, the nine contrasts (placebo, nocebo and control condition by pain anticipation, pain administration and pain rating) with the fixation (baseline) will each be calculated using a general linear model.

Group analysis will be performed using a random-effects model. A full factorial module in SPM 8 will be performed to test the differences between the inert Lidocaine, Capsaicin and control creams during pain anticipation, application and intensity ratings separately within each group; then we will compare the differences (between the Lidocaine and control, and Capsaicin and control) among the three groups (tDCS inhibition, tDCS enhancement and sham tDCS) to investigate how tDCS can modulate the placebo and nocebo effects. Covariates including LOT, ERS, STAI scores, gender, and experimenter effect will also be included in the model.

In addition, a multiple regression analysis will be performed between the placebo and nocebo effects as indicated by subjective pain rating differences and corresponding fMRI signal differences by pooling the data of all three groups (group indicator will be included in the model as a covariate). Covariates will include LOT, ERS, STAI scores, gender, and experimenter effect. As in previous studies [2, 4-6], a threshold of voxel-wise $p < 0.005$ with 20 contiguous voxels will be used for pre-defined ROIs. For non-ROI, a threshold of voxel-wise $p < 0.005$ and cluster level $p < 0.05$ Family-wise Error (FWE) corrected will be used.

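### Aim 2 spells out connectivity comparisons that read as within-group, although Hypothesis 2 is a comparison with sham; the sham contrasts should be named as its test

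*SAP*

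**What the plan says.** The protocol's Hypothesis 2 (Specific Aim 2) is comparative. Enhancement is expected to raise rDLPFC connectivity with the rACC and insula, while inhibition "will decrease rsFC between the rDLPFC and rACC and insula as compared with sham tDCS".

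The SAP's Specific Aim 2 group analysis specifies a full factorial model with "three groups (excitability enhancement, inhibition and sham), two tDCS (first and third) with two conditions (pre and post-treatment") as factors. From that model it spells out two comparisons:

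- "To investigate the incremental effect across the first and last tDCS", the SAP states "we will compare pre- and post-treatment differences in tDCS 1 and 3 of each group".
- For the build-up over the stimulation days, "we will also apply the same analysis on the pre-tDCS rsFC in tDCS 1 and 3".

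It then adds a regression, pooled over the three groups, of pain-rating differences on connectivity after the third stimulation. That regression serves the association sentence of Hypothesis 2, not the comparison with sham. The threshold of p<0.005 "will be applied for the region of interest"; the section does not say whether it applies to voxels or to an ROI mean.

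**The concern.** The comparator in the hypothesis does not appear in the comparisons that the SAP writes out. If these are carried out within each group, a change over time in an active arm could be reported as an effect of stimulation even when sham subjects changed by the same amount.

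Shared changes are plausible in this design. Between sessions, from the scan before the first stimulation to the scan before the third, every arm has been scanned before, and at the start of Session 5 every subject is told that the Session 2 procedure will be repeated. Within a session, the two resting scans are separated by 20 minutes of real or sham stimulation in the scanner. Only a contrast against sham removes what the arms have in common.

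**Working it through.** **Step 1. Set the two aims side by side.** The SAP's Aim 1 group analysis has two written steps. The first compares the creams "during pain anticipation, application and intensity ratings separately within each group". The second compares the resulting cream differences across the inhibition, enhancement and sham groups. Aim 2 has the three-group model and the comparisons quoted above, but no second step. The stated purpose of its first comparison, change from the first to the last stimulation, also points to a comparison made inside each group. The words can be read as comparing the groups' differences, but that is the less natural reading.

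**Step 2. Illustrate the risk of within-group testing.** The plan gives no effect size, SD or power for Aim 2, so there is no figure to reproduce.

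- From the documents: n = 26 per group (protocol, Study Procedures); threshold 0.005 (SAP, Aim 2).
- Assumed: two-sided test, one ROI-mean test per arm, independent arms, and the same true standardised change d in active and sham, so no stimulation effect.

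The one-sample t test has 25 df, critical value 3.078 and noncentrality d√26. Call its power p. The chance that a given active arm is significant and sham is not is p(1−p).

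| d | p | p(1−p) |
|---|---|---|
| 0 | 0.005 | 0.005 |
| 0.1 | 0.010 | 0.010 |
| 0.2 | 0.031 | 0.030 |
| 0.3 | 0.082 | 0.075 |
| 0.4 | 0.178 | 0.146 |
| 0.5 | 0.324 | 0.219 |
| 0.6 | 0.505 | 0.250 |
| 0.8 | 0.828 | 0.142 |
| 1.0 | 0.970 | 0.029 |

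Example at d = 0.5: noncentrality 0.5 × 5.099 = 2.55, p = 0.324, and 0.324 × 0.676 = 0.219. The direct active-minus-sham test rejects with probability 0.005 at every d, because the shared change cancels. A simulation of 200,000 trials per d gave 0.0046 to 0.0051 for the direct test and agreed with the table.

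**Step 3. Price the direct contrast.** The two-sample t test with 26 per group has 50 df, critical value 2.937 and noncentrality d√13, where d is now the assumed between-group difference in SDs of the change. Power is 0.141, 0.486 and 0.744 at d = 0.5, 0.8 and 1.0, and reaches 80% at d = 1.054. Pooling error over all three groups (78 − 3 = 75 df) gives 0.147, 0.501 and 0.759.

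**The case against.** The strongest reply is that the test is already planned at model level. Sham is a level of the group factor, group by pre/post is an interaction in the fitted model, and a three-group factor has little purpose if groups are never compared. This stands. A reader might infer that sham is left out or that Hypothesis 2 is not tested; the documents do not support either. The gap lies in which comparisons are written out, not in the model.

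Three limits on the consequence also stand:

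- If the first comparison sets the change at the third stimulation against the change at the first, drift that is equal in both sessions subtracts out even within a group. The 20 minutes in the scanner is then a weak source of bias. The comparison of the two pre-stimulation scans has no such protection and is the clearest case.
- A reader might take 0.22 to 0.25 as the plan's false-positive rate. No passage says that an effect will be claimed when an active arm is significant and sham is not, and no d is documented. The figures cover one arm in either direction. The full pattern of Hypothesis 2, a rise under enhancement and a fall under inhibition, is not what a shared change produces: with no change its chance is 0.0025 × 0.0025 = 0.000006, and a shared change makes it smaller.
- The SAP's ROI threshold for Aim 1 is voxel-wise. If Aim 2's is too, none of these figures is an ROI-level rate.

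None of this supplies the missing contrast. Aim 1 shows that the SAP writes out a between-group step when it intends one.

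**Conclusion.** The point holds as a mismatch between a hypothesis stated against sham and written comparisons that read most naturally as within-group. That sham is absent from the comparisons spelled out is certain; how the analyst would apply the wording is not.

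On the within-group reading, a change shared with sham could be credited to stimulation, most clearly from the first to the last pre-stimulation scan. Under the assumptions in the working, the illustrative risk for one arm and one test runs from 0.01 at a shared change of 0.1 to a maximum of 0.25 at 0.6, and falls again beyond that. At 0.1 or less the excess over 0.005 is at most about 0.005, so the issue is material only for moderate shared changes.

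It should be fixed because it bears on the Aim 2 primary outcome and the remedy is nearly free. The unstated session and the reference to "To investigate the incremental effect across three time points", when only two pre-stimulation scans exist because Session 4 has none, are points of detail that add no weight.

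**What to change.** Amend the SAP's Aim 2 group analysis, using the model already planned:

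1. Name enhancement-minus-sham and inhibition-minus-sham in post-minus-pre connectivity, for rACC and insula, as the test of Hypothesis 2. Fix in advance whether the first stimulation session, the third, or their average is used.
2. Test both incremental contrasts as differences from sham: the change in the pre/post difference from the first to the third stimulation, and the change between the two pre-stimulation scans.
3. Report within-group changes descriptively.

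No scan, subject or model is added. The price is a more demanding test: with 26 per group, a single test and two-sided 0.005, 80% power needs a standardised between-group difference of about 1.05, and at 0.5 the power is only 0.14. That should be stated openly. It is not a reason to rest Hypothesis 2 on within-group results, which do not answer it.

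### Aim 2 primary outcome: the only rule for rACC and insula is p<0.005, with no test unit, extent or correction stated, and the contrasts with sham are not named

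*SAP*

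**What the plan says.** The SAP, under Specific Aim 2, declares "Primary outcome: rDLPFC functional connectivity changes before and after different tDCS intervention". The hypothesised targets are in the protocol, Hypothesis 2: "Enhancing rDLPFC excitability will increase resting state functional connectivity (rsFC) between the rDLPFC and rACC and insula", with a decrease under inhibition, both relative to sham. That hypothesis also predicts an association between rDLPFC–rACC connectivity and the placebo effect, without giving its direction.

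For the group analysis the SAP says "A full factorial model module in SPM8 will be applied", with three groups, two tDCS sessions (first and third) and pre/post conditions. The comparisons it spells out are:

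- "we will compare pre- and post-treatment differences in tDCS 1 and 3 of each group";
- "we will also apply the same analysis on the pre-tDCS rsFC in tDCS 1 and 3";
- regressions of the placebo and nocebo effects on "rsFC after the third tDCS by pooling the data of all three groups".

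The section ends with two threshold rules. For the hypothesised regions: "A threshold of $p < 0.005$ will be applied for the region of interest". For everything else: "A threshold of $p < 0.001$ uncorrected and $p < 0.05$ corrected will be used for non-ROI brain areas".

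**The concern.** The requirement of a corrected p-value is attached only to areas outside the regions of interest. The regions that carry the primary outcome have a bare p<0.005. What that controls depends on the unit of test. One test on a region mean at 0.005 is strict. A search over every voxel in rACC and insula, where a single voxel below 0.005 counts, has no stated error rate, and the rate rises with region size and the number of contrasts.

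The group model contains the cells needed for enhancement against sham and inhibition against sham, but the text does not name those contrasts or say whether they use the first session, the third or both. No adjustment can be set until that family of tests is fixed. As written, both the unit of test and the contrasts could be chosen after the maps are seen.

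**Working it through.** The documents give no family-wise error rate or power figure for Aim 2, so there is no stated figure to reproduce. The check asks what p<0.005 delivers under each reading when tDCS has no effect.

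**Inputs from the documents.** p<0.005 (SAP, Aim 2); two regions, rACC and insula, and two contrasts with sham (protocol, Hypothesis 2), hence four tests; 26 per group (protocol, Study Procedures).

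**Assumptions not in the documents.** Spherical regions of 2–20 cm³; effective smoothness 8–12 mm; voxels of 2–3 mm; one direction per test (z>2.576); the two regions independent; contrasts with sham taken on the third-session change. The SAP applies 6 mm smoothing; assuming a smoother map lowers the rates.

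**Reading 1: voxel-wise, no extent.** Smooth Gaussian null fields were simulated for the three groups, with sham shared by both contrasts. Let p1 be the chance of at least one positive voxel for one contrast in one region, and p2 the chance for either contrast in one region. Any of four = 1 − (1 − p2)².

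| Setting | p1 | p2 | Any of four |
|---|---|---|---|
| 2 cm³, 12 mm, 3 mm voxels (lowest) | 0.060 | 0.122 | 1 − 0.878² = 0.229 |
| 10 cm³, 8 mm, 3 mm voxels | 0.428 | 0.673 | 1 − 0.327² = 0.893 |
| 10 cm³, 8 mm, 2 mm voxels | 0.510 | 0.772 | 1 − 0.228² = 0.948 |
| 20 cm³, 8 mm, 2 mm voxels (highest) | 0.717 | 0.924 | 1 − 0.076² = 0.994 |

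The rate exceeds 50% in 17 of the 24 settings. If the two regions were fully dependent, the range would be 12%–92%.

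*All four as predicted.* The chance that both contrasts are positive in one region is 2·p1 − p2, and all four is its square. A separate simulation at 10 cm³ and 8 mm gave p1 = 0.41, p2 = 0.67 (3 mm voxels) and 0.49, 0.77 (2 mm voxels). Then (0.82 − 0.67)² = 0.15² = 0.022, and (0.98 − 0.77)² = 0.21² = 0.044. This is a small difference of simulated rates, so it is good to only a point or two; about 2%–5% is a fair summary.

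**Reading 2: voxel-wise with Aim 1's 20-voxel extent carried over.** Same null model. Any of four at 10 cm³ and 8 mm: about 2% with 3 mm voxels and about 30% with 2 mm voxels. Twenty voxels are 20 × 27 = 540 mm³ in the first case and 20 × 8 = 160 mm³ in the second.

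**Reading 3: one test per region mean.** Rate = 1 − 0.995^k, tests taken as independent.

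- Four contrasts with sham: 1 − 0.995⁴ = 2.0%.
- The ROI tests the SAP spells out. Per region: three session 1-versus-3 comparisons of the pre/post change (one per group), three on pre-tDCS connectivity, and two regressions, making 8. Over two regions that is 16, and 1 − 0.995¹⁶ = 7.7%.
- The 5% level is kept up to 10 tests (4.9%) and passed at 11 (5.4%).

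**The case against.** The strongest reply is that the text is silent rather than wrong, and that silence has benign readings. On region means, p<0.005 is adequate for the four contrasts. Aim 1 of the same SAP pairs p<0.005 with a 20-voxel extent; if that was meant here, the rate may be near or below nominal. Both points stand as possibilities. Neither is stated: no region averaging is described for Aim 2, the Aim 2 text does not refer to the Aim 1 rule, and its non-ROI threshold (p<0.001) already differs from Aim 1's (p<0.005). Even with the extent, the rate depends on a voxel size and region volume that the SAP does not give.

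It is also fair that every voxel-wise rate rests on assumed volume, smoothness and voxel size, and that much smaller regions would lower it: at 0.5 cm³ the rate per region and contrast is about 3%–10%.

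Four stronger inferences are tempting, and the documents do not support them.

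- *That the SAP declares the ROI test uncorrected.* It does not use that word for the ROI; it says nothing either way.
- *That Hypothesis 2 would be falsely confirmed about nine times in ten.* The 89%–95% figure is for any one of four contrasts. The hypothesis predicts a joint pattern, and all four arising by chance is far rarer.
- *That the contrasts with sham belong in the count of planned tests.* The SAP does not spell them out, so the count from its text is 16.
- *That Aim 1's ROI rule is too lenient.* It states a unit and an extent, and nothing here shows that it fails.

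**Conclusion.** The point holds. The regions that carry a declared primary outcome have a threshold whose false-positive rate cannot be determined from the plan. On the natural reading of the text, voxel-wise on an SPM8 map with no extent, the chance of at least one false-positive contrast with sham is not controlled: about 23%–99% over the assumed settings, and 89%–95% at 10 cm³ and 8 mm. On the other two readings, at that same setting, it is about 2% or 30% (20-voxel extent, by voxel size) and about 2% (region mean).

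Confidence is high that the unit, extent, correction and contrasts are unstated. The size of the harm is conditional on the assumptions listed. The pain-rating outcome and the non-ROI tests are not affected. This should be fixed before the connectivity maps are analysed.

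**What to change.** Replace the Aim 2 ROI rule with one of two options: small-volume FWE-corrected p<0.05 within rACC and insula masks fixed before analysis, or one declared ROI-mean test per region and contrast.

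In either case, name the confirmatory Hypothesis 2 tests and the session used: enhancement against sham and inhibition against sham in each region, in the directions the protocol already gives, plus the connectivity–placebo regression in rACC with its direction stated. That is five tests. Apply a multiplicity adjustment such as Holm across them, and report any other p<0.005 ROI maps as exploratory.

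**Cost.** SAP wording, two masks and a threshold option in the same software; no new data. Small-volume correction loses sensitivity. With 26 per group, the difference in pre/post change that gives 50% power at one voxel is d = z·√(2/26) = z/√13. At 10 cm³ and 8 mm:

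- present rule, z = 2.576: 0.71 SD;
- small-volume FWE 5%, z = 3.44–3.53: 0.95–0.98 SD;
- Holm's first step over five tests (0.05/5 = 1%), z = 3.92–3.99: 1.09–1.11 SD.

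For the regression, with 78 subjects and about seven covariate terms assumed, r = tanh(z/√68): the partial correlation for 50% power rises from 0.30 to about 0.40, and to 0.44–0.45 at Holm's first step.

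The ROI-mean option is not stricter than the present level, since Holm's first step is 0.01 against 0.005 (0.65 SD against 0.71 SD), but averaging dilutes a focal effect.
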